Captopril	100 mg	Candesartan	16 mg
Cilazapril	2.5 mg	Eprosartan	400 mg
Enalapril	10 mg	Irbesartan	150 mg
Fosinopril	20 mg	Losartan	50 mg
Imidapril	10 mg	Olmesartan	10 mg
Lisinopril	10 mg	Telmisartan	40 mg
Moxepril	7.5 mg	Valsartan	160 mg
Perindopril	4 mg		
Quinapril	20 mg		
Ramipril	5 mg		
Trandolapril	2 mg		
Zofenopril	30 mg		

Randomized treatment epoch

At the end of treatment run-in, patients who meet the protocol specified safety criteria as assessed by central or local laboratories and tolerate LCZ696 100 mg bid for at least 2 weeks are eligible for randomization. Patients will be randomized in a 1:1 fashion to either LCZ696 200 mg bid or valsartan 160 mg bid. The randomization will be stratified based on age (< 75, ≥ 75 years), MMSE score (< 28, ≥ 28), and baseline brain amyloid status (unknown, amyloid positive, amyloid negative).

With an expected screening and run-in failure rate of approximately 40%, it is estimated that approximately 870 patients will be screened at more than 150 centers worldwide to randomize approximately 520 patients. A subset of about 430 randomized patients will be enrolled in the amyloid PET imaging substudy.

There is no formal interim analysis planned for efficacy. Interim safety data will be reviewed by an external Data Monitoring Committee (DMC) regularly as specified in the DMC charter. The final analysis is planned to be executed at the completion of all planned assessments for last randomized patient.

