2.5.2 Statistical hypothesis, model, and method of analysis

The change from baseline in the GCCS of CogState test battery will be analyzed using a repeated measures analysis of covariance (ANCOVA) model in which treatment, age stratification factor, MMSE stratification factor, education level, APOE4 status (carrier vs. non-carrier), baseline cerebrovascular disease burden, visit (Weeks 26, 52, 78, 104, 130 and Week 156) and treatment-by-visit interaction are included as fixed-effect factors and baseline GCCS and visit-by-baseline GCCS interaction as covariates, with a common unstructured covariance matrix among visits between treatment groups. The adjusted mean changes at 3 years (Week 156) within each treatment, the difference in mean changes at 3 years (Week 156) between the two treatments, and its 95% confidence interval obtained from the above model will be presented. In addition, the treatment difference (LCZ696-valsartan) in mean changes from baseline to 3 years will also be expressed based on a standardized effect size (Cohen's d) with a 2-sided 95% confidence interval. The Cohen's d will be estimated by using the adjusted between-treatment mean difference, divided by the estimated pooled standard deviation. The estimated standard deviation for the mean difference is:

$$SD = \left(\frac{1}{n_1} + \frac{1}{n_2} \right)^{1/2} \hat{\sigma}$$

where n1 and n2 are the number of patients within each treatment group and $\hat{\sigma}$ is the pooled standard deviation of the within treatment group adjusted mean change. Cohen's d can be rewritten in terms of t value of the estimated between treatment group difference based on the adjusted mean changes from the model mentioned above:

$$t = \frac{\hat{\mu}_1 - \hat{\mu}_2}{SD} = \frac{\hat{\mu}_1 - \hat{\mu}_2}{\left(\frac{1}{n_1} + \frac{1}{n_2} \right)^{1/2} \hat{\sigma}}$$

$$\hat{d} = \frac{\hat{\mu}_1 - \hat{\mu}_2}{\hat{\sigma}} = \left(\frac{1}{n_1} + \frac{1}{n_2} \right)^{1/2} \times t$$

Confidence interval (CI) of Cohen's d is based on 95% CI of the noncentrality parameter of t value divided by the square root of the degrees of freedom from the estimated between treatment group adjusted mean change (Cumming and Finch 2001). The analysis is based on a direct likelihood method with an assumption of missing at random (MAR) for the missing data mechanism.

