As the primary analysis, the repeated measure ANCOVA model will be performed in the Safety set including 'on-treatment' data (section 2.1.1) collected prior to the start of treatments for AD or cognitive impairment. The Cohen's d based on the adjusted difference in mean changes at 3

years (Week 156) between two treatments and its 95% confidence interval from this model will be used to draw the main conclusion for the primary objective. As defined in [section 2.1.1](#), on-treatment data refer to cognitive test data collected while patients are on-study-medication (regardless of treatment interruption) or within three months after final study drug intake date.

When above mentioned model does not converge, the primary analysis model will be modified by replacing the common unstructured covariance matrix with a compound symmetry covariance matrix between treatment groups and provide above mentioned estimates. If convergence issue remains after implementing the compound symmetry covariance matrix, the model will be simplified by removing baseline cerebrovascular disease burden as explanatory factor from the model.

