3.1 Sample size calculation for the primary endpoint

It is currently estimated that approximately 180 patients per group having data on 3-year planned follow up –

- Would provide at least 80% probability that the 2-sided 95% confidence interval (CI) excludes a standardized effect size (Cohen's d) of 0.3 (or greater) in change in composite z-score of the battery test over 3 years, given that there is no expected difference between two treatments.
- Would provide at least 80% probability that the 2-sided CI excludes 0 (corresponding to $p < 0.05$), if the true effect size is 0.3 or greater (in either direction).

An effect size of 0.3 in Cohen's d corresponds to a margin of $0.3 \times SD$ ($SD =$ standard deviation) on the original scale for the difference between treatments in mean global score change from baseline, and is generally considered as small (Cohen 1988). In a systematic review of studies for health-related quality of life instruments that have reported the minimally important difference (MID), it was found that for the majority of studies the MID estimates were consistently close to $0.5 \times SD$ (Norman et al 2003). In addition, socially accepted benchmarks for conditions that induce cognitive impairment such as low level alcohol intoxication within legal driving limit in most countries (0.05%) are generally associated with declines of 0.3 or higher for psychomotor speed, attention and working memory. Therefore, the sample size of the study was determined to be able to detect (or exclude) effect sizes in the magnitude of 0.3 in Cohen's d with high probability, as it appears to be an appropriate choice to guide the interpretation of the cognitive function results.

In addition, defining the magnitude of the MID using a measure of effect size, rather than a raw difference score has additional advantages:

- Expressing the magnitude of an important difference in scale free units (Cohen's d) allows models of clinically meaningful difference to be based on integration of outcomes from a broad set of studies whose characteristics are relevant to the current study (i.e. magnitude of change in cognition related to amyloid, magnitude of change occurring after heart failure, and magnitude of change related to cardiovascular disease).

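### The SD that converts the Week 156 difference into Cohen's d is not tied to the SD behind the 0.3 margin, so the plan does not fix which GCCS difference 0.3 excludes

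*SAP*

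**What the plan says.** SAP 2.5.2 fits a repeated-measures model to change in GCCS with treatment, age and MMSE strata, education, APOE4 status, cerebrovascular burden, visit, treatment-by-visit, and baseline GCCS with its visit interaction. It then sets d = t × √(1/n1 + 1/n2), where t belongs to the adjusted Week 156 difference. The implied denominator "is the pooled standard deviation of the within treatment group adjusted mean change", and n1 and n2 are only called the numbers of patients per group. Protocol 9.4.2 likewise builds the SD from the standard error of the adjusted mean change and the group size, so a model-derived SD is prespecified in both documents.

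SAP 2.5.2 adds that d for the Week 156 difference "between two treatments and its 95% confidence interval from this model will be used to draw the main conclusion for the primary objective". If the model does not converge, compound symmetry replaces the unstructured covariance, and then cerebrovascular burden is dropped.

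The margin is explained elsewhere. SAP 3.1, in the same terms as protocol 9.8.1, equates d = 0.3 with 0.3 × SD "on the original scale for the difference between treatments in mean global score change from baseline". Both sections defend scale-free units partly because these let results from many different studies be combined.

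**The concern.** Two scales are in play. The planning text reads as though 0.3 were measured in SDs of the change in GCCS. The analysis measures it in an SD recovered from a standard error that has already been reduced by the covariates and that is multiplied back up by an undefined n. When these SDs differ, a CI that excludes 0.3 in the analysis excludes a different GCCS difference from the one the margin describes.

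The analysis yardstick is also not settled in advance. Prognostic covariates shrink it. Compound symmetry would impose one residual variance on all visits, and dropping cerebrovascular burden would change the covariate set. Counting patients without Week 156 data in n1 and n2 would enlarge it. Even the covariate list varies: the protocol summary includes region, while protocol 9.4.2 and SAP 2.5.2 do not. At stake is what a reader may conclude, in GCCS terms, from the trial's headline statement.

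**Working it through.** **Inputs from the documents.** SAP 3.1: "approximately 180 patients per group having data on 3-year planned follow up", two-sided 95% CI, margin d = 0.3, at least 80% probability, "given that there is no expected difference between two treatments". SAP 1.1: "Patients will be randomized in a 1:1 fashion". SAP 3.3 and protocol 9.8.3: about 520 randomised, 30% information loss.

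**Assumptions (not in the documents).** Correlation ρ between baseline and Week 156 GCCS of 0.6 to 0.8; ratio k of Week 156 to baseline SD equal to 1, varied in step 6; other covariates explaining R² = 0 to 0.10 of the variance left after baseline.

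1. *The plan's own figure.* P(exclude 0.3 | no difference) = Φ(0.3 × √(180/2) − 1.96) = Φ(2.846 − 1.96) = Φ(0.886) = 0.812. The noncentral t gives 0.812, and 0.810 for excluding 0 when d = 0.3. The n for 80% is 175 per group (176 with the t distribution). 360/0.70 = 515, in line with 520. The plan's figures reproduce.

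2. *Width of the CI for d.* With d = t × √(1/n1 + 1/n2), the half-width near d = 0 is 1.96 × √(2/180) = 0.207. No SD or R² enters, so the 0.812 does not move with the covariates. A single-visit ANCOVA simulation (six covariates, 180 per group, 4,000 runs per setting, total R² from 0 to 0.4) gave 0.81 to 0.82 throughout.

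3. *What 0.3 means in SDs of change, complete data.* Var(residual given baseline)/Var(change) = (1 − ρ²)/(2(1 − ρ)) = (1 + ρ)/2, then multiplied by (1 − R²).

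| ρ | R² | SD ratio | 0.3 in SD of change | Inflation of d |
|---|---|---|---|---|
| 0.8 | 0 | √0.90 = 0.949 | 0.285 | 1/0.949 = 1.05 |
| 0.6 | 0.10 | √(0.80 × 0.90) = 0.849 | 0.255 | 1/0.849 = 1.18 |

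4. *Exclusion probability if the margin is held at 0.3 SD of change.* Φ(2.846/ratio − 1.96): 2.846/0.949 = 3.00 gives Φ(1.04) = 0.85; 2.846/0.849 = 3.35 gives Φ(1.39) = 0.92. Against 0.81 in step 1, this is what adjustment would contribute on that scale.

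5. *Effect of n1 and n2.* Suppose all randomised patients are counted (520/2 = 260 per group) while the standard error reflects information worth 180. The back-calculated SD is inflated by √(260/180) = 1.20. The margins in step 3 become 0.255 × 1.20 = 0.306 and 0.285 × 1.20 = 0.342 SD of change. The probability of excluding nominal 0.3 becomes Φ(0.3 × √(260/2) − 1.96) = Φ(1.46) = 0.93.

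6. *If variance grows over three years.* R² of change on baseline = (1 − ρk)²/(1 + k² − 2ρk). At ρ = 0.8 this is 0.10 for k = 1, 0.03 for k = 1.1 and 0 for k = 1.25, so the shrinkage due to baseline can vanish.

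These probabilities take the CI on the same scale as d. SAP 2.5.2 instead describes dividing the noncentrality limits by the square root of the degrees of freedom. With 358 degrees of freedom (two groups of 180) that gives a half-width of 1.96/√358 = 0.104, about half of 0.207. This is a separate inconsistency with the formula for d, and it has to be resolved in the same paragraph.

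**The case against.** The strongest reply is that the plan does not contradict itself. A reader might infer an explicit clash between the margin and the analysis. The documents do not support that: neither sample-size section says the SD is unadjusted, and protocol 9.4.2, in the same document as the margin, prespecifies a model-derived SD. The benchmarks offered for 0.3 (a conventional small effect, a minimally important difference near 0.5 SD, low-level alcohol effects) are not tied to the SD of three-year change either. This stands. What remains is an untied yardstick, and the stated reason for scale-free units, comparability across studies, is not served by a residual SD specific to this model.

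Second, the covariate effect alone costs nothing that was promised. The plan claims at least 80% and obtains 81%, and a smaller GCCS margin is the stricter choice for a no-harm claim. This also stands, but only with complete data or with n1 and n2 matched to the information; step 5 reverses the direction.

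Third, the size of the shrinkage rests on assumed correlations and equal variances. Agreed; step 6 shows that it can disappear.

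Fourth, the adjusted GCCS difference and its CI are reported anyway. True, but the main conclusion is drawn from d.

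A reader might also infer that every added covariate shrinks the margin. Only prognostic ones do: six non-prognostic covariates left the simulated margin at 0.302. Nor is adjustment without use, since for a fixed GCCS difference it still helps to exclude 0.

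**Conclusion.** The point holds as a gap in definition. With complete data, nominal 0.3 corresponds to about 0.255 to 0.285 SD of change, and adjustment leaves the exclusion probability at 81%, against 85% to 92% if the margin sat on the SD of change. With all randomised patients as n1 and n2 and information worth 180 per group, it corresponds to about 0.31 to 0.34 SD. These ranges rest on the assumed correlation, equal variances and R², none of which the documents give, and on reading the margin's SD as the SD of change.

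Two stronger conclusions are tempting and not supported. One is that the sample size is wrong: 180 per group and 80% reproduce without any covariate gain. The other is that covariate adjustment makes exclusion too easy: by itself it makes it stricter, and any loosening comes from the choice of n1 and n2.

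**What to change.** In SAP 2.5.2, keep the adjusted Week 156 difference and its CI from the full model. Obtain d and its CI by dividing both by the pooled within-arm SD of the Week 156 change. Take that SD from the estimated covariance matrix of a repeated-measures model with only treatment, visit and treatment-by-visit, not from a standard error multiplied by √n. This keeps the likelihood handling of missing data under MAR and removes the dependence on the covariate list and on n1 and n2. State in advance what is done if this second model does not converge, in a way that leaves the Week 156 variance free.

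Replace the square-root-of-degrees-of-freedom wording so that the CI is on the scale of d. Use the same denominator for the secondary endpoints in SAP 2.6.2 and in step 4 of the tipping-point analysis in SAP 2.5.5. Show the residual-SD version of d as a secondary display. Record the departure from protocol 9.4.2 in SAP section 4, which now reports no changes.

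The cost is SAP wording, the documented change and one extra model fit. For a given GCCS difference, |d| will be about 5% to 15% smaller than with the complete-data residual SD (1 − 0.949 and 1 − 0.849). The rescaled CI also ignores the small uncertainty in the SD itself.

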1. Multiple (e.g. 100) imputations of missing GCCS values under a MAR assumption are generated, resulting in multiple (100) complete data sets. This imputation is based on predicted GCCS values from the fitted repeated measures ANCOVA model for the GCCS values (at baseline, Weeks 26, 52, 78, 104, 130 and Week 156) with treatment, age group (<75, ≥75 years), baseline MMSE status (<28, ≥28), baseline cerebrovascular disease burden, visit and treatment-by-visit interaction as factors having fixed effects assuming a common unstructured covariance matrix among visits between treatment group. SAS proc MI FCS statement is used to impute missing values in the following sequence: factor variables in the increasing order of missing frequency, the GCCS at baseline, Weeks 26, 52, 78, 104, 130 and Week 156.
2. For each completed data set, the imputed GCCS values at a given visit for patients who died, or had a HF hospitalization or stroke since the preceding visit, a penalty factor would be applied to the imputed values to reflect that the MAR approach may have overestimated the missing values, e.g. by assuming the actual GCCS values could be a certain percentage (e.g. 5%) worse than MAR based imputations for discontinuations due to death, HF hospitalization and stroke. If the MAR-imputed GCCS value is positive, the final value will be 95% x the imputed value; if the MAR-imputed GCCS value is negative, the final value will be 105% x the imputed value.
3. The primary analysis model as described above will be fitted to the 100 completed data sets following the application of the penalty factor in step 2 which produces 100 sets of parameter estimates and associated covariance matrices.
4. These 100 sets of parameter estimates are then combined by using Rubin's rules to derive overall estimates and their confidence intervals. In a similar manner to the primary analysis, a standardized effect size estimate (Cohen's d) and 95% CI will also be reported using the pooled SD.

The analysis will be repeated for varying penalty factors in a range between 0 and 50%. It is performed using 'on-treatment' data in the SAF, as done in the primary analysis. Tipping point analyses will be performed separately to assess the sensitivity of the results to MAR assumptions under the following situations:

- for missing data due to censoring at the start of AD and cognitive impairment treatments, including on-treatment data only in the SAF

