2.6.2 Statistical hypothesis, model, and method of analysis

For secondary efficacy variables composite z-scores by individual domain (memory, executive function and attention) and IADL, the changes from baseline to 3 years will be analyzed using the same repeated measures ANCOVA model as described in [Section 2.5.2](#) but with baseline GCCS replaced with respective secondary variable baselines. The adjusted mean changes at 3 years (Week 156) within each treatment, the difference in mean changes at 3 years (Week 156) between two treatments, its 95% confidence interval obtained from the above model will be presented. In addition, the treatment difference (LCZ696-valsartan) in mean changes from baseline to 3 years will also be expressed in terms of a standardized effect size (Cohen's d) with a 2-sided 95% confidence interval. The Cohen's d will be estimated as in a similar manner as planned for the primary endpoint analysis ([Section 2.5.2](#)). The analysis is based on likelihood method with an assumption of missing at random for missing data, and will be performed in the Safety set including 'on-treatment' data collected prior to the start of treatments for AD or cognitive impairment. On-treatment data are those collected while patients are on-study-

medication (regardless of treatment interruption) or within three months after final study drug intake date. This analysis will be performed in the SAF.

In addition, as supportive analysis, similar repeated measure ANCOVA model will also be performed for these secondary endpoints for all data in the FAS.

Summaries of absolute values and change from baseline by treatment group and visit will be presented. Figures will be produced to visually show the endpoint values (composite z scores by cognitive domain and IADL) by visit over the study period for each treatment group.

These analyses will be done in both SAF and FAS, for 'on-treatment' data and for all data, respectively.

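### SAP 2.5.2 puts Cohen's d and its 95% CI on different scales: at 180 per group both limits come out about 40% to 50% too small (assumed df 250 to 358)

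*SAP*

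**What the plan says.** SAP 2.5.2 takes the Week 156 treatment difference (LCZ696 minus valsartan) from the repeated measures model and divides it by a pooled SD. It notes that d "can be rewritten in terms of t value of the estimated between treatment group difference", which gives d = sqrt(1/n1 + 1/n2) × t, "where n1 and n2 are the number of patients within each treatment group".

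For the interval it changes the multiplier. The CI for d is based on the "95% CI of the noncentrality parameter of t value divided by the square root of the degrees of freedom" belonging to the adjusted treatment contrast. No value or method is given for those df. Protocol 9.4.2 describes only the point estimate and its pooled SD, so nothing elsewhere corrects the SAP sentence.

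For the primary analysis, d and "its 95% confidence interval from this model will be used to draw the main conclusion for the primary objective". SAP 3.1 sizes the trial to detect or exclude a d of 0.3, with "approximately 180 patients per group having data on 3-year planned follow up", and keeps 0.3 "as it appears to be an appropriate choice to guide the interpretation of the cognitive function results". For the secondary efficacy endpoints (SAP 2.6.2), d "will be estimated as in a similar manner as planned for the primary endpoint analysis". In the tipping point analysis (SAP 2.5.5, step 4), the d estimate "and 95% CI will also be reported using the pooled SD".

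**The concern.** An estimate and its confidence limits must be on the same scale. If d is t times a constant, the limits for the population d are the limits for the noncentrality parameter times that same constant. Dividing by sqrt(df) uses a different constant. The two agree only if df = n1·n2/(n1 + n2), which is 90 at 180 per group. A two-group comparison of that size would have n1 + n2 - 2 = 358.

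The trial asks whether neprilysin inhibition could harm cognition, and 0.3 SD is the size of effect the plan wants to be able to rule out. Limits pulled toward zero make it too easy to appear to have ruled it out. A true decline of 0.3 SD on LCZ696 could be reported as lying outside the interval.

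**Working it through.** **Inputs**
- n = 180 per group with 3-year data, and a reference d of 0.3 (SAP 3.1).
- d = t × sqrt(1/n1 + 1/n2), and CI limits = noncentrality limits / sqrt(df) (SAP 2.5.2).
- Allocation 1:1, 520 randomized (SAP 1.1).
- Assumption: df of 250, 300 or 358, where 358 = 2 × 180 - 2.

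**The plan's own figure.** With 180 per group, the probability that a 2-sided 95% CI excludes 0 at true d = 0.3 is 81.0% (noncentral t, df 358). The SAP states at least 80%, so its sizing reproduces, but only with the multiplier sqrt(2/180).

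**Scale factors.** Correct factor: sqrt(2/180) = 0.1054. For equal arms, the ratio of the written factor to the correct one is sqrt(n/(2·df)).

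| df | 1/sqrt(df) | Ratio | Limits too small by |
|---|---|---|---|
| 250 | 0.0632 | 0.60 | 40% |
| 300 | 0.0577 | 0.55 | 45% |
| 358 | 0.0529 | 0.50 | 50% |

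**Effect on the interval.** The noncentrality limits come from inverting the noncentral t distribution.
- Observed d = -0.10 gives t = -0.10/0.1054 = -0.949. At df 358 the noncentrality limits are -2.909 and 1.013. Multiplied by 0.1054 they give -0.31 to 0.11. Divided by sqrt(358) = 18.92 they give -0.15 to 0.05. So -0.3 moves from inside the interval to outside it.
- Observed d = -0.30 gives t = -2.846. Correct: -0.51 to -0.09. As written: -0.31 to -0.05 (df 250), -0.28 to -0.05 (df 300), -0.25 to -0.05 (df 358).
- The written interval fails to contain its own point estimate once |d| exceeds about 0.31, 0.25 or 0.21 (df 250, 300, 358).

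**Effect on reading the interval against 0.3.** The lower limit reaches -0.3 at an observed d of -0.093 when scaled correctly. As written, this happens only at -0.292, -0.340 or -0.390 (df 250, 300, 358).

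| Probability that the CI excludes -0.3 | Correct | df 250 | df 300 | df 358 |
|---|---|---|---|---|
| True d = -0.3 | 2.5% | 47% | 64% | 80% |
| True d = 0 | 81% | 99.7% | 99.9% | 99.99% |

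Dividing 0.3 by the ratio shows what the reference value becomes on the true d scale: 0.50, 0.55 and 0.60. Coverage at true d = -0.3 is 53% (df 250) and 20% (df 358), against 95%.

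**Other readings of n and df**

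| n per group | df | Ratio | Excludes -0.3 at true d = -0.3 |
|---|---|---|---|
| 260 (randomized) | 200 | 0.81 | 13% |
| 260 | 250 | 0.72 | 26% |
| 260 | 358 | 0.60 | 61% |
| 260 | 518 | 0.50 | 92% |
| 180 | 500 | 0.42 | 97% |

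The shrinkage is present in every case; its size is not fixed by the documents.

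**The case against.** Five points can be made for the plan.

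- The sentence says the CI is based on this quantity and cites a methods paper. A programmer following the derivation just above could scale the limits correctly, and the code is not available. This stands as a limit on what is shown: the defect is in the SAP text. But division by sqrt(df) is the only operation written, and anyone who follows it gets the wrong interval.
- The 40% to 50% depends on df and n, neither of which the SAP pins down. This also stands. The cases above run from 19% to 58%. None removes the error or reverses its direction.
- The plan sets no non-inferiority margin and no test against 0.3, so the exclusion probabilities are illustrations and not formal error rates. That is fair. The SAP nevertheless uses 0.3 to size the trial and to guide interpretation, and this is the interval against which it would be read.
- The unstandardized difference and its model-based CI are also reported and are sound. True, but SAP 2.5.2 names the CI for d as the basis for the main conclusion.
- SAP 2.5.5 and 2.6.2 do not repeat the faulty sentence. They would take it over only through their references to the primary method.

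**Conclusion.** The concern holds. As written, the CI for Cohen's d is on a different scale from d and is shrunk toward zero. At 180 per group and an assumed df of 250 to 358, both limits are 40% to 50% too small, and a reported exclusion of 0.3 means exclusion of only about 0.5 to 0.6. The existence and direction of the error follow from the SAP's own formula for d at any plausible df; the exact size rests on the assumed n and df. Because both limits keep their sign, the conclusion about zero does not change. This must be corrected, since the interval carries the primary conclusion.

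**What to change.** Replace the CI sentence in SAP 2.5.2 with: *The 95% CI for d is obtained by multiplying the lower and upper 95% limits of the noncentrality parameter of t by sqrt(1/n1 + 1/n2), the same factor used for the point estimate.*

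In the same place:
- State which patients n1 and n2 count. One option is those with a Week 156 GCCS in the primary analysis, which matches the sizing basis in SAP 3.1. The choice also affects the point estimate.
- State the df source and method for the Week 156 contrast.
- Say that the same rule applies to the secondary endpoints (2.6.2) and the tipping point estimates (2.5.5), and name the df used after Rubin's rules.

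Cost: a few sentences and a short code check, with no new data. The reported interval becomes about 1.7 to 2 times wider (1/0.60 to 1/0.50), which is the precision the trial was sized for.
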